APTT	Activated partial thromboplastin time
█	█
AST	Aspartate aminotransferase
ATG	Anti-thymocyte globulin
AUC _{0-t}	Area under the serum concentration-time curve from time 0 to the last detectable time
BUN	Blood urea nitrogen
CI	Confidence Interval
█	█
C _{max}	Maximum serum concentration
CMML	Chronic myelomonocytic leukemia
Cr	Creatinine
CTCAE	Common Terminology Criteria for Adverse Events
D-Bil	Direct bilirubin
ECG	Electrocardiogram
ECOG	Eastern Cooperative Oncology Group
eCRF	Electronic case report form
EDC	Electronic data capture
FAS	Full Analysis Set
γ-GTP	γ-glutamyl transpeptidase
GCP	Good Clinical Practice, international standards for conducting clinical studies.
G-CSF	Granulocyte-colony stimulating factor
GPI-cell	Glycosyl phosphatidyl inositol-cell
Hb	Hemoglobin
█	█
Ht	Hematocrit
ICF	Informed Consent Form
IFN-γ	Interferon-γ
IST	Immunosuppressive therapy
ITP	Idiopathic (Immune) Thrombocytopenic Purpura
IRB	Institutional review board
IWRS	Interactive Web Response System
LIN	Lineage
LDH	Lactate dehydrogenase
NYHA	New York Heart Association
MCH	Mean corpuscular hemoglobin
MCHC	Mean corpuscular hemoglobin concentration

ABBREVIATION	DEFINITION
MCV	Mean corpuscular volume
MDS	Myelodysplastic syndromes
MedDRA	Medical Dictionary for Regulatory Activities
██████	████████████████████
███	████████████████████
███	████████████████████
██████████	██
PNH	Paroxysmal nocturnal hemoglobinuria
PPS	Per Protocol Set
PS	Performance status
PT-INR	Prothrombin time - International Normalized Ratio
PTs	Preferred Terms
RBC	Red blood cell
Ret	Reticulocyte
SDP	Single Donor Platelet
SID	Subject identification
SOC	System Organ Class
T-Bil	Total bilirubin
T-Cho	Total cholesterol
TIBC	Total iron-binding capacity
TMP	Thrombopoietin mimetic peptide
TNF- α	Tumor necrosis factor- α
T _{max}	Time to reach maximum serum drug concentration
TP	Total protein
TPO	Thrombopoietin
TSAT	Transferrin saturation : $TSAT = Fe \times 100 / TIBC$
UA	Uric acid
UIBC	Unsaturated iron-binding capacity
WBC	White blood cell

DEFINITION OF TERMS

Platelet Response

Platelet response is defined as (1) Absolute increase of $\geq 20 \times 10^9/L$ above baseline or, (2) Increase to $\geq 10 \times 10^9/L$ and by at least 100% from baseline.

Erythroid Response

Erythroid response is defined in those who with a pretreatment hemoglobin of < 9.0 g/dL as an increase in hemoglobin concentration of ≥ 1.5 g/dL above baseline without transfusion, or reduction in the transfusion unit by at least 4 units for 8 consecutive weeks compared with the pretreatment transfusion requirement in the previous 8 weeks prior to the first administration of AMG531 (Day -55 to Day 1).

Neutrophil Response

Neutrophil response is defined in those with a pretreatment absolute neutrophil count (ANC) of $< 0.5 \times 10^9/L$ as a 100% increase over the baseline, or an increase in ANC of $> 0.5 \times 10^9/L$ in subjects with a pretreatment ANC of $< 1.0 \times 10^9/L$.

Baseline

Baseline values are defined as the values obtained before dosing AMG531 on Study Day 1. Data obtained during the screening period will serve as baseline values for those not measured or reported on Study Day 1. If multiple evaluations are performed during the screening period for a particular test, with the exception of platelet count, the values measured closest to the first administration of AMG531 will be considered as the baseline values (if hemoglobin concentration at Study Day 1 is within 28 days after RBC transfusion, hemoglobin concentration determined during the screening period will be used as baseline hemoglobin).

Baseline Platelet Count

Baseline platelet count is defined as the mean of two lowest platelet counts measured in 8 weeks prior to enrollment. Platelet count that is obtained within 7 days after platelet transfusion will not be used. The baseline platelet according to the definition of protocol Master Ver1.1 (The mean of two lowest platelet counts measured in 8 weeks prior to enrollment. Platelet count that is obtained within 3 days after platelet transfusion will not be used.) will be also collected .

Platelet Transfusion

Platelet transfusion given due to platelet count of $< 10 \times 10^9/L$ (prophylactic transfusion) or due to bleeding (therapeutic transfusion).

RBC Transfusion

RBC transfusion given due to the hemoglobin concentration of ≤ 9.0 g/dL or due to symptomatic anemia

Adverse Drug Reaction

Adverse events of which causal relationship to the investigational product cannot be ruled out (any events assessed to be other than “unlikely” or “not related”).

Study Duration

Study duration of each subject in this study is specified as the period from the day of obtaining written informed consent through the end of examinations on completion of treatment (or withdrawal).

Observation and Examination Period

In this study, Week 1 (Day 1) is defined to be the day of initial administration of AMG531. Initial dose evaluation period is defined to be the period from Week 1 to Week 8, Extension period is the period from Week 9 to Week 52, and Long-term treatment period is the period from Week 53 to Week 156.

Aplastic Anemia with Refractory Thrombocytopenia

Aplastic anemia with thrombocytopenia defined as platelet count of $\leq 30 \times 10^9/L$ that does not respond to the immunosuppressive therapy (ATG + cyclosporine), or relapsed after having showed response.

Transfusion Independence

Achieving platelet or RBC transfusion free period of at least 8 consecutive weeks.

Tri-lineage response

Tri-lineage response is defined in those achieving platelet response, erythroid response, and neutrophil response all together.

Normal level

Normal level is defined as platelet counts $>50 \times 10^9/L$, hemoglobin concentration >10.0 g/dL, and neutrophil counts $>1.0 \times 10^9/L$

Stable response

Stable response is defined as platelet counts $\geq 30 \times 10^9/L$, hemoglobin concentration ≥ 9.0 g/dL, and neutrophil counts $\geq 0.5 \times 10^9/L$ maintained during dose tapering or discontinuation without transfusion

Cytogenetic abnormality

Any cytogenetic abnormalities newly emerged during or after the initiation of AMG531 treatment

PROTOCOL SYNOPSIS

I TITLE

A phase 2, Randomized, Open-Label, Parallel, Comparative, Dose-Finding Study to Evaluate the Efficacy and Safety of AMG531 in Aplastic Anemia (AA) Subjects with Thrombocytopenia Refractory to Immunosuppressive Therapy

[figure not shown]
II STUDY OBJECTIVES

The present study will be conducted to evaluate the efficacy and safety of AMG531 and to determine the recommended initial dose of AMG531 on the basis of its efficacy and safety when it is administered SC, QW at a dose of 1, 3, 6 or 10 $\mu\text{g}/\text{kg}$ to the aplastic anemia patients with immunosuppressive-therapy refractory thrombocytopenia and also to assess the pharmacokinetics of this product during the initial dose evaluation period. Its efficacy and safety during the extension period will also be evaluated. Efficacy and safety of AMG531 in the long term treatment beyond 1-year will be further evaluated for those showing continuous responses after 1 year treatment.

III STUDY DESIGN

This is a multi-center, randomized, open-label, parallel, comparative, dose-finding study.

The overall study design is presented below.

IV STUDY SUBJECTS

AA subjects with thrombocytopenia refractory to immunosuppressive agents.

IV-1 Inclusion criteria

Subjects may be included in the study if they meet all of the following criteria:

- 1) Patients who have provided written informed consent of their free will to participate in this clinical study. Written informed consent must be obtained prior to performing any study-related procedure
- 2) The subject is able and willing to comply with study procedures and follow-up as described in the protocol and ICF
- 3) Males and female subjects ≥ 19 years of age at the time of obtaining informed consent
- 4) Eastern Cooperative Oncology Group (ECOG) performance status (PS) score of ≤ 2 at the time of screening
- 5) Diagnosis of AA, confirmed by bone marrow and cytogenetic studies
- 6) Patient who is refractory to immunosuppressive therapy (IST)
- 7) Prior treatment with at least one course of horse or rabbit anti-thymocyte globulin (ATG) with cyclosporine
- 8) Thrombocytopenia defined as platelet $\leq 30 \times 10^9/L$
- 9) Fulfilling all of the following criteria in the screening examination
 - T-Bilirubin ≤ 1.5 times the upper limit of the laboratory normal range
 - ALT and AST ≤ 3 times the upper limit of the laboratory normal range
 - Creatinine ≤ 2.0 mg/dL

IV-2 Exclusion criteria

Subjects must be excluded from participating in this study if they meet any of the following criteria:

- 1) Concurrent active infection not adequately responding to appropriate therapy
- 2) Human immunodeficiency virus positivity
- 3) Bone marrow reticulin grade of > 1 (Appendix 1)
- 4) Previous or concurrent active malignancies other than localized tumors diagnosed more than one year previously and treated surgically with curative intent (basal cell carcinoma or surgically resected in situ carcinoma of the cervix with apparent success ≥ 12 months prior to enrollment, as well as other cancers which have not been treated or have remained disease-free for at least 3 years before enrollment are eligible)
- 5) Clinically significant cardiac disease (class III or IV of the New York Heart Association (NYHA) classification; unstable angina pectoris; myocardial infarction)

within 6 months or is post angioplasty or stenting within 6 months; uncontrolled hypertension; clinically significant cardiac arrhythmia)

- 6) Arterial or venous thrombosis within the last 1 year before enrollment
- 7) Other cause of thrombocytopenia (for instance MDS, ITP, liver cirrhosis)
- 8) Subjects with AML or CMML
- 9) AA with hemolytic predominant PNH (hemolytic predominant is defined as LDH > 1.5 times the upper limit of the laboratory normal range)
- 10) Uncontrolled diabetes
- 11) Receiving other investigational agents within 16 weeks before starting the study treatment
- 12) Receiving any agent used to treat AA, including ATG or ATG + cyclosporine within 6 months before starting study treatment and/or cyclosporine or anabolic hormone within 6 weeks before starting the study treatment
- 13) History of PEG-rHuMGDF, recombinant human thrombopoietin, AMG531, and other TPO-receptor agonist
- 14) Who plans to conduct hematopoietic stem cell transplantation within 1 year
- 15) Known hypersensitivity to any recombinant *E. Coli* derived product
- 16) Female subjects who are nursing or pregnant or are unwilling to take oral contraceptives or refrain from pregnancy if of childbearing potential
- 17) Subjects who are considered to be ineligible for the study by the investigator for reasons other than the above

V DOSE, DOSING SCHEDULE, AND TREATMENT DURATION

There must be at least 3 days between the doses of AMG531 in each subject.

V-1 Initial dose evaluation period (Week 1 to Week 8)

AMG531 will be administered at a dose of 1, 3, 6 or 10 µg/kg SC QW for 8 weeks. Dose adjustment (either escalation or reduction) will not be allowed during the initial dose evaluation period except for the cases defined in the V-4 Criteria for discontinuing and resuming study treatment.

V-2 Extension period (Week 9 to Week 52)

Initial dose of AMG531 for the extension period will be decided based on the efficacy and safety data observed during the initial dose evaluation period. If a subject does not show a platelet response at Week 9, the dose will be increased by one level according to Table V-1. AMG531 dose adjustment (extension period) table. If no platelet measurement is available due to the platelet transfusion, then that week's platelet response is considered as having no response.

- 1) Dose escalation

Dose escalation will be allowed during the extension period. If a subject does not show a platelet response after 4-week treatment with AMG531 at the previously escalated dose, the dose may be further increased by one level according to Table V-1 at the discretion of the investigator, with the highest dose being 20 µg/kg. The necessity and timing of dose escalation after 4 week administration at a previously escalated dose will be decided by investigator after thorough consideration of the relevant safety and efficacy data for each subject.

2) Dose adjustment

If a subject shows a platelet response, the dose may be adjusted as appropriate to maintain the platelet response at the discretion of the investigator referring to the relevant efficacy and safety data of the each subject. For each dose adjustment, dose may be increased or decreased only by one level at a time according to the Table V-1, with the highest dose being 20 µg/kg.

Table V-1 AMG531 Dose adjustment table (extension period)

AMG531 Dose
1 µg/kg
3 µg/kg
6 µg/kg
10 µg/kg
13 µg/kg
16 µg/kg
20 µg/kg

V-3 Long-term treatment period (Week 53 to Week 156)

1) Initial Dose

AMG531 will be administered SC QW at the same dose received as the last dose in the extension period. If dose adjustment is deemed to be necessary at Week 53 by investigator, the dose may be adjusted according to the Table V-2 Dose adjustment (long-term treatment period) table.

2) Dose adjustment

The dose may be adjusted as appropriate to maintain the platelet response at the discretion of the investigator. For each dose adjustment, dose may be increased or decreased only by one level at a time according to the Table V-2, with the highest dose being 20 µg/kg and the lowest dose being 3 µg/kg.

Table V-2 AMG531 Dose adjustment (long-term treatment period)

AMG531 Dose
3 µg/kg
6 µg/kg
10 µg/kg
13 µg/kg
16 µg/kg
20 µg/kg

3) Tapering and Discontinuation

If tri-lineage is maintained within normal level for 8-consecutive weeks with the same dose without transfusion, the dose will be decreased by one level at every 4 weeks. If tri-lineage is maintained within normal level for 4 consecutive weeks with 3 µg/kg without transfusion, AMG531 will be discontinued.

Normal level is defined as platelet counts $>50 \times 10^9/L$ and hemoglobin concentration >10.0 g/dL and neutrophil counts $>1.0 \times 10^9/L$.

While tapering, if platelet counts drop to less than $30 \times 10^9/L$, hemoglobin to less than 9.0 g/dL, or neutrophil counts to less than $0.5 \times 10^9/L$, the tapering has to be stopped and dose will be adjusted following section V-3 2). If the study drug were discontinued, it will be resumed at a dose of 3 µg/kg and further adjusted in accordance with section V-3 2). Tapering may be tried again at the discretion of investigator.

While tapering, if patient does not meet the criteria of further tapering but maintains steady stable response, the dose will be kept stable. During tapering, dose reduction should follow section V-3 3), not V-3 2). While discontinuation, if patient maintains the steady stable response, dosing will not be resumed.

V-4 Criteria for discontinuing and resuming study treatment

If the platelet has exceeded $400 \times 10^9/L$ during the treatment period, study treatment will be temporarily discontinued. Once the platelet count falls to $< 200 \times 10^9/L$, administration of AMG531 will resume at a reduced dose by one level according to the protocol. Once the platelet count falls to $\leq 50 \times 10^9/L$ during the treatment with reduced dose by one level, dosing will be resumed at the temporarily discontinued dose.

If the platelet has exceeded $200 \times 10^9/L$ during the treatment period, the dose of AMG531 will be reduced to the next lower dose tested. If the temporarily discontinued dose is 1 µg/kg, treatment will be resumed at the dose of 1 µg/kg.

Other than the reasons above, investigator can reduce the dose at any time during the study if safety concerns arise.

VI STUDY ENDPOINTS

VI-1 Efficacy

1) Primary endpoint

The proportion of subjects achieving a platelet response at Week 9.

2) Secondary endpoints

- The proportion of subjects achieving a platelet response any time during the initial dose evaluation period, Week1 through Week 12, Week 1 through Week 16, Week 1 through Week 24, and Week 1 through Week 52
- The proportion of subjects who become platelet transfusion independent during the initial dose evaluation period, Week1 through Week 12, Week 1 through Week 16, Week 1 through Week 24, Week 1 through Week 52, Week 1 through Week 104, and Week1 through Week 156
- The proportion of subjects achieving erythroid response and/or neutrophil response during the initial dose evaluation period, Week1 through Week 12, Week 1 through Week 16, Week 1 through Week 24, Week 1 through Week 52, Week 1 through Week 104, and Week1 through Week 156
- Duration of platelet response
- Time to platelet response
- Changes in platelet count, hemoglobin concentration, and neutrophil count as continuous variables
- Changes in bone marrow cellularity and reticulin grade
- Changes in GIMEMA bleeding scale
- The proportion of subjects achieving tri-lineage responses
- The proportion of subjects able to discontinue study drugs after achieving normal level for 8 consecutive weeks without transfusion.
- Duration of study drug discontinuation while maintaining stable response

VI-2 Pharmacokinetics

- Serum AMG531 concentration
- Pharmacokinetic parameters

VI-3 Safety

- Adverse events
- Antibody formation against AMG531 and TPO

VI-4 Exploratory

- The changes of primitive hematopoietic stem and progenitor cells
- The changes of progenitor cell pool (colony forming cell assay)
- The changes of stromal cell (colony forming unit fibroblast assay)
- Cytokine assay (IL-2, IL-6, IL-10, IL-12, IL-17, IFN- γ , TNF- α)

VII CRITERIA FOR SUBJECT WITHDRAWAL

Any of the following circumstances will result in the subject being withdrawn from the study:

- 1) The subject is found to be ineligible for participation in this study due to violations in the inclusion or exclusion criteria specified in the study protocol;
- 2) The subject decides to discontinue his/her participation in the study;
- 3) The subject becomes unable to undergo necessary observations or examinations;
- 4) The subject who does not achieve a platelet response after 8-week treatment with AMG531 20 $\mu\text{g}/\text{kg}$ QW;
- 5) The investigator considers that the subject should be withdrawn from the study due to an adverse event (including progression of the primary disease);
- 6) The subject received any of the prohibited concomitant medications or treatments;
- 7) The subject becomes pregnant or wants to have children during the study;
- 8) The investigator assesses that the subject needs to be withdrawn from the study for any reason not specified above;
- 9) The subject who does not meet the entry criteria for long-term treatment period

VIII TARGET SAMPLE SIZE

1) Efficacy and Safety

Eight in each cohort, a total of 32 subjects receiving AMG531 at a dose of 1, 3, 6 or 10 $\mu\text{g}/\text{kg}$ during the initial dose evaluation period will be assessed for the primary endpoint.

[figure not shown]
2) Pharmacokinetics

Serum concentrations of AMG531 will be determined in 3 subjects in each cohort, a total of 12 subjects (in chronological order of enrollment) receiving AMG531 at a dose of 1, 3, 6 or 10 $\mu\text{g}/\text{kg}$.

IX PLANNED STUDY PERIOD

January 2014 to March 2018

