5.3 Exclusion criteria

Subjects must be excluded from participating in this study if they meet any of the following criteria:

- 1) Concurrent active infection not adequately responding to appropriate therapy
- 2) Human immunodeficiency virus positivity
- 3) Bone marrow reticulin grade of > 1 (Appendix 1)
- 4) Previous or concurrent active malignancies other than localized tumors diagnosed more than one year previously and treated surgically with curative intent (basal cell carcinoma or surgically resected in situ carcinoma of the cervix with apparent success ≥ 12 months prior to enrollment, as well as other cancers which have not been treated or have remained disease-free for at least 3 years before enrollment are eligible)
- 5) Clinically significant cardiac disease (class III or IV of the New York Heart Association (NYHA) classification; unstable angina pectoris, myocardial infarction within 6 months or is post angioplasty or stenting within 6 months; uncontrolled hypertension, clinically significant cardiac arrhythmia)
- 6) Arterial or venous thrombosis within the last 1 year before enrollment

- 7) Other cause of thrombocytopenia (for instance MDS, ITP, liver cirrhosis)
- 8) Subjects with AML or CMML
- 9) AA with hemolytic predominant PNH (hemolytic predominant is defined as LDH > 1.5 times the upper limit of the laboratory normal range)
- 10) Uncontrolled diabetes
- 11) Receiving other investigational agents within 16 weeks before starting the study treatment
- 12) Receiving any agent used to treat AA, including ATG or ATG+cyclosporine within 6 months before starting study treatment and/or cyclosporine or anabolic hormone within 6 weeks before starting the study treatment
- 13) History of PEG-rHuMGDF, recombinant human thrombopoietin, AMG531, and other TPO-receptor agonist
- 14) Who plans to conduct hematopoietic stem cell transplantation within 1 year
- 15) Known hypersensitivity to any recombinant *E. coli* derived product
- 16) Female subjects who are nursing or pregnant or are unwilling to take oral contraceptives or refrain from pregnancy if of childbearing potential
- 17) Subjects who are considered to be ineligible for the study by the investigator for reasons other than the above

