6.2.2 Prohibited medications and therapies

While on study treatment, subjects are not permitted to receive any additional experimental medication or any therapy known or suspected to affect platelet production and AA from the time of enrollment throughout the study period. Examples of prohibited medications or therapies are follows;

- 1) Any investigational agents other than AMG531
- 2) TPO agonist other than AMG531

- 3) Other drugs to treat AA or symptoms associated with AA (e.g., immunosuppressive agents, cyclosporine, growth factors [For the case of G-CSF, its administration is only permitted as a rescue medication to treat infection, and will be prohibited for the purpose of treating AA])
- 4) Any medication known or suspected to affect platelet production
- 5) Hematopoietic stem cell transplantation

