12.1.1 Efficacy

Platelet count measured within 7 days after platelet transfusion will not be subjected to the efficacy assessment. Likewise, hemoglobin concentrations determined within 28 days after RBC transfusion will not be subjected to the efficacy assessment. Neutrophil counts determined within 7 days of G-CSF as a rescue medication will not be used for the efficacy assessment.

Platelet count, hemoglobin concentrations and neutrophil counts determined in occasions other than in the scheduled visit in this study, including ordinary medical examinations and follow-up, will not be used for efficacy assessment.

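### Baseline ANC has no stated G-CSF rule and no named replacement, so a G-CSF-raised baseline can make neutrophil and tri-lineage response harder to reach, or unreachable at 1.0 × 10^9/L or more

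*Combined protocol and SAP*

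**What the plan says.** **Baseline.** The main rule in Definition of Terms is that "Baseline values are defined as the values obtained before dosing AMG531 on Study Day 1". Screening data step in only for values that were not taken or not recorded that day. With several screening evaluations, "with the exception of platelet count, the values measured closest to the first administration of AMG531 will be considered as the baseline values". Hematology is scheduled before dosing at Week 1 (section 8.2.2), so the Day 1 rule will normally govern ANC.

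**Protection for the other two lineages.** For hemoglobin the Baseline entry adds that "if hemoglobin concentration at Study Day 1 is within 28 days after RBC transfusion, hemoglobin concentration determined during the screening period will be used". For platelets, the Baseline Platelet Count entry says "Platelet count that is obtained within 7 days after platelet transfusion will not be used". No such clause exists for ANC.

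**Efficacy data rules.** Section 12.1.1 says "Neutrophil counts determined within 7 days of G-CSF as a rescue medication will not be used for the efficacy assessment". Section 6.2.1 more generally removes counts taken after rescue medication thought to affect them, with no time window.

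**Who may have had G-CSF.** Exclusion 1 (section 5.3) bars only "Concurrent active infection not adequately responding to appropriate therapy". Exclusion 12 covers agents used to treat AA, naming ATG with a 6-month window, "and/or cyclosporine or anabolic hormone within 6 weeks before starting the study treatment"; G-CSF is not named. From enrollment, section 6.2.2 says of G-CSF that "its administration is only permitted as a rescue medication to treat infection", and bars it as treatment for AA. Section 7 allows up to 7 days between enrollment and the first dose.

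**Response.** Neutrophil response needs either a pretreatment ANC below 0.5 × 10^9/L and a doubling, or a pretreatment ANC below 1.0 and a rise of more than 0.5. Tri-lineage response requires neutrophil response.

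**The concern.** Section 12.1.1 has three parallel exclusions: platelets after transfusion, hemoglobin after transfusion, and ANC after G-CSF. The definitions mirror the first two at baseline but not the third.

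The plan therefore treats an ANC shortly after rescue G-CSF as uninformative after baseline, yet has no stated rule against using the same kind of value as the reference for every later ANC. A stimulated baseline would be compared with later counts from which rescue-G-CSF values have been removed.

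What is at stake is the neutrophil response proportion, the tri-lineage proportion that depends on it, and the summary of ANC change from baseline. All are secondary endpoints.

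**Working it through.** The plan states no figure to reproduce here: section 12.2 sets no significance level, and the sample size is given without derivation. The check is of the definitions. ANC is in units of 10^9/L.

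**Step 1. Can G-CSF precede the Day 1 ANC within 7 days?** Yes. Section 6.2.2 permits it for infection from enrollment, and section 7 puts the first dose at most 7 days later, so any G-CSF given between the two lies within 7 days of the Day 1 sample. This route does not depend on how exclusion 12 is read. Before enrollment, exclusion 1 admits a subject whose infection is responding to therapy, and exclusion 12 does not clearly cover G-CSF given for infection, a use that section 6.2.2 separates from treating AA.

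**Step 2. What happens to that ANC?** There are two readings.
- Baseline entry taken alone: the stimulated Day 1 value is the baseline.
- Sections 6.2.1 and 12.1.1 applied to Day 1: the value is unusable. The screening fallback does not apply, because the value was both taken and recorded, and section 12.4 rules out imputation. The subject has no ANC baseline.

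**Step 3. Lowest ANC that counts as response, for recorded baseline b.**
- b < 0.5: the doubling limb gives 2b, which is below b + 0.5, so the target is ≥ 2b.
- 0.5 ≤ b < 1.0: the target is > b + 0.5.
- b ≥ 1.0: neither limb applies.

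For an assumed unstimulated ANC of 0.3:

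| Recorded baseline | Target |
|---|---|
| 0.3 (no G-CSF effect) | 2 × 0.3 = 0.6 or more |
| 0.45 | 2 × 0.45 = 0.9 or more |
| 0.6 | above 0.6 + 0.5 = 1.1 |
| 0.8 | above 0.8 + 0.5 = 1.3 |
| 1.0 or more | none |

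The multiplier that lifts baseline to 1.0 is 1.0 divided by the unstimulated value: 10 for 0.1, 5 for 0.2, 2.5 for 0.4, 1.67 for 0.6, 1.25 for 0.8. The documents give no G-CSF effect size, so every raised value here is an assumption.

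**Step 4. Change from baseline.** If the true ANC goes from 0.3 to 0.7, the true change is 0.7 − 0.3 = +0.4, and the subject is a responder (0.7 ≥ 0.6). With baseline recorded as 0.8, the change is 0.7 − 0.8 = −0.1, and the subject is not.

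**Step 5. Effect on an arm of 8.** Section 12.1.1.1 asks for a two-sided 95% interval without naming a method; Clopper-Pearson is used here. Start from an illustrative 4/8 = 50% (15.7 to 84.3).
- A would-be responder stays in and counts as a failure: 3/8 = 37.5% (8.5 to 75.5), a shift of 1/8 = 12.5 points.
- A would-be responder leaves the denominator: 3/7 = 42.9% (9.9 to 81.6).
- A would-be non-responder leaves the denominator: 4/7 = 57.1% (18.4 to 90.1).

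The plan does not say which applies, so neither the direction nor the size of the shift is fixed.

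**The case against.** The strongest reply is that the plan already covers this. Section 6.2.1 defines rescue medication by purpose, including anything given to raise neutrophils, and speaks of the whole study period. Study Duration in Definition of Terms starts at consent. On that reading, G-CSF given during screening to raise neutrophils is rescue, and the affected ANC is unusable. Section 12.1.1 is not confined to post-baseline values either. A reader might infer that baseline ANC has no protection at all; the documents do not support that. What survives is narrower: these rules do not mention baseline, do not clearly reach G-CSF given before consent or enrollment, and name no replacement value.

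Exclusion 12 can also be read widely. Its general phrase covers agents used to treat AA, and section 6.2.2 lists growth factors among drugs for AA or its symptoms. That may bar G-CSF given for AA. It does not clearly bar G-CSF given for infection, and it has no bearing on the interval from enrollment to Day 1.

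On harm, a reader might infer that response becomes impossible and the proportions are biased downward. Impossibility holds only at a recorded baseline of 1.0 × 10^9/L or more, which needs a 5- to 10-fold rise from an ANC of 0.1 to 0.2; below 1.0 the target is higher but reachable. A downward shift of 12.5 points presumes a would-be responder kept in a denominator of 8. An erythroid responder would still count if the erythroid and/or neutrophil endpoint is reported as a composite.

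Finally, section 12.5 leaves detail to an analysis plan finalized before database lock. That is an opportunity to add the rule. In an open-label study it is better fixed in advance than settled case by case under section 12.4.

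**Conclusion.** The concern holds as a gap in the baseline definition. Followed as written, the plan gives a subject with G-CSF in the week before Day 1 either a stimulated ANC baseline or no usable one, and does not say which.

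A stimulated baseline raises the bar for neutrophil and tri-lineage response and distorts ANC change. From 1.0 × 10^9/L upward it removes any chance of response, or removes the subject from the denominator.

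The size per subject rests on assumed G-CSF effects. How many of the 32 subjects would be affected cannot be derived from the documents. The Week 9 platelet endpoint is untouched, and the affected endpoints are secondary and descriptive, with no significance level. This is worth correcting, but it does not threaten the trial's main conclusion.

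**What to change.** 1. **Baseline (Definition of Terms).** Add, in parallel with the hemoglobin clause: *an ANC measured within 7 days after any G-CSF is not used as baseline; the latest screening ANC not within 7 days after G-CSF is used instead.*
2. **Section 12.1.1.** State that the 7-day G-CSF rule applies to baseline and post-baseline ANC, whatever the reason for G-CSF. After enrollment the broader wording changes little, since only rescue use is permitted; its main effect is on earlier G-CSF.
3. **Section 6.2.1.** Align the open-ended rescue-medication rule with the 7-day window for ANC.
4. **Data collection.** Record G-CSF dates at screening. Section 8.2.1 lists concomitant medications without asking for dates, and section 6.2.3 requires treatment duration only after enrollment.
5. **Denominator.** State whether subjects with a baseline ANC of 1.0 × 10^9/L or more, or with no usable baseline, leave the neutrophil and tri-lineage denominators or count as non-responders.

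The cost is a few sentences and one added data item. Section 8.2.1 already includes screening hematology and allows retesting, so a replacement may often exist. The downside is that a few subjects will use an earlier screening ANC, or have no ANC baseline if none is free of G-CSF.
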